receiving placebo reported dry eye (n=1). All eye disorders AEs were of mild to moderate intensity, resolved spontaneously (without treatment), and were more frequently reported with highest dose (40 mg). Among them, the AEs of blurred vision, photophobia (“Increased ocular light sensitivity”), visual impairment (“distorted contrast perception”, “distorted colour perception”) reported by 8 out of 47 subjects receiving emodepside were considered as treatment-related by the Investigator. Also of note, at the highest dose (40 mg), lightheadedness (n=1), dizziness (n=1) or headache (n=1) were reported concomitantly to blurred vision.

None of the volunteers met any of the protocol-specified withdrawal criteria and overall tolerability to emodepside has been acceptable up to 20 mg. The presence of post-dose visual disturbances in subjects of Cohort 8 receiving either 40 mg solution or placebo may warrant some concern and escalation was stopped at this dose level.

The pharmacokinetic results obtained so far show that T_{max} for the LSF solution is consistently about 1 h post-dose when fasted. Mean C_{max} and AUC for the LSF solution have been roughly dose-proportional, with low to moderate inter-individual variability. The plasma half-life during the first 24 h is very short for a single dose of emodepside. After 3, 7, 16 and 47 h the maximum plasma concentration is reduced to 50%, 25%, 12.5% and 6.25% respectively. Terminal plasma half-life is 523 h. Although data of Cohort 9 (which was treated with a single dose of emodepside with food) are still under review, administration of the LSF of 10 mg with a high fat, high-calorie meal resulted in a clinically relevant food effect with a reduction of AUC to ~67%, C_{max} to 42% and a delay of the T_{max} up to 2.33 h. Therefore, the recommendation of administration of the emodepside (LSF) under fasted conditions is given.

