14.6.5 Ophthalmology examination

Abnormal ophthalmology examination findings will be listed.

15 Pharmacokinetic Analyses

Analytical Services International Ltd will measure the plasma concentrations of emodepside. The pharmacokinetic analysis will be done by Statistics and Data Management Department at HMR. Pharmacokinetic parameters will be calculated using WinNonlin, version 7.0 or higher.

The pharmacokinetic parameters to be derived are given in Appendix B.

PK concentration data will be summarised using the PK concentration population. PK parameters will be summarised using the PK parameter population.

For log normally distributed parameters, the primary measure of central tendency will be the geometric mean⁴; for other parameters, it will be the arithmetic mean or median.

For all variables N (number of subjects receiving the treatment/formulation in the population), n (number of observations), arithmetic mean, median, minimum, maximum, SD, %CV, and the 95% confidence interval for the arithmetic mean will be provided. For log-transformed variables, all of the above plus the geometric mean, which is the anti-logged arithmetic mean of log-transformed variables, its 95% confidence interval and the SD of the logs will be provided.

The between-subject CV will be calculated using:

1. $\%CV_b = 100 * (SD/Mean)$ with SD and Mean of untransformed data

2. $\%CV_b = 100 * \sqrt{\exp(SD)^2 - 1}$ with SD of log-transformed data

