18 ATTACHMENTS

18.1 Table of Contents for Data Display Specifications

For overall page layout refer to Appendix C.

Tables, figures and listings will be labelled A (for Cohorts 1 and 2) and B (for Cohort 3), e.g. 14.1A, 14.1B. Separate tables will be produced for Cohorts 1 and 2 and for Cohort 3.

The numbering in the tables below will take precedence over the numbering in the shells.

The following tables and figures will be produced (templates provided in Section 18.2.1):

Table	Description	Population	Source Listing	Template (Shells below)
10.1	Summary of subject disposition	Safety	16.2.1.2, 16.2.3.1	T_SD1
14.1	DEMOGRAPHIC DATA			
14.1	Summary of demographic characteristics	Safety	16.2.4.1	T_DM1
14.2	PHARMACOKINETIC AND PHARMACODYNAMIC DATA			
14.2.1.1	Summary of emodepside plasma pharmacokinetic concentration-time data [units]	PK Concentration	16.2.6.1.1	T_PK1
14.2.1.2	Summary of derived emodepside plasma pharmacokinetic parameters	PK Parameter	16.2.6.1.2	T_PK3
14.2.1.3	Summary of log-transformed derived emodepside plasma pharmacokinetic parameter	PK Parameter	16.2.6.1.2	T_PK4
14.2.2.1	Summary of glucose	Safety	16.2.6.2.1	T_LB2
14.2.2.2	Summary of insulin	Safety	16.2.6.2.1	T_LB2
14.2.2.3	Summary of glucagon	Safety	16.2.6.2.1	T_LB2
14.2.2.4	Summary of cortisol	Safety	16.2.6.2.1	T_LB2
14.2.3.1	Summary of oral glucose tolerance test results	Safety	16.2.6.2.1	T_LB2
14.3	SAFETY DATA			
14.3.1.1	Summary of treatment-emergent adverse events	Safety	16.2.7.1	T_AE1
14.3.1.2	Summary of drug-related treatment-emergent adverse events	Safety	16.2.7.1	T_AE1
14.3.1.3	Summary of treatment-emergent adverse events by severity	Safety	16.2.7.1	T_AE3
14.3.2.1	Listing of fatal adverse events	Safety	16.2.7.1	L_AE1_PG
14.3.2.2	Listing of non-fatal serious adverse events	Safety	16.2.7.1	L_AE1_PG
14.3.2.3	Listing of other significant adverse events	Safety	16.2.7.1	L_AE1_PG
14.3.3	Narratives of deaths, other serious and significant adverse events	Safety		-
14.3.4	Summary of laboratory values of potential clinical importance	Safety	16.2.8.1, 16.2.8.3	T_LB1
14.3.5.1	Summary of chemistry laboratory values	Safety	16.4	T_LB2
14.3.5.2	Summary of haematology laboratory values	Safety	16.4	T_LB2
14.3.5.3	Summary of coagulation laboratory values	Safety	16.4	T_LB2
14.3.5.4	Summary of urinalysis results	Safety	16.2.8.5	T_UR1

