		30 min	x	x	xxxx.x	(xxxx.x,xxxx.x)	xx.xx	xx.x	xxxx.x	xxxx	xxxx		
		1 hr	x	x	xxxx.x	(xxxx.x,xxxx.x)	xx.xx	xx.x	xxxx.x	xxxx	xxxx		

Source: Listing 16.2.xx

Programming notes: Continued with all dose levels and timepoints

Template T_PK3

Table 14.2.xx Summary of derived emodepside plasma pharmacokinetic parameters

Parameter	Treatment	{Additional time variables}	n	Mean	95% CI (Lower,Upper)	SD	%CVb	Median	Min	Max
AUC _t (units)	Treatment 1 (N=xx)		xx	xxxx.xx	(xxxx.xx,xxxx.xx)	xx.xxx	xx.x	xxxx.xx	xxxx.x	xxxx.x
	Treatment 2 (N=xx)		xx	xxxx.xx	(xxxx.xx,xxxx.xx)	xx.xxx	xx.x	xxxx.xx	xxxx.x	xxxx.x
C _{max} (units)	Treatment 1 (N=xx)		xx	xxxx.xx	(xxxx.xx,xxxx.xx)	xx.xxx	xx.x	xxxx.xx	xxxx.x	xxxx.x
	Treatment 2 (N=xx)		xx	xxxx.xx	(xxxx.xx,xxxx.xx)	xx.xxx	xx.x	xxxx.xx	xxxx.x	xxxx.x

Source: Listing 16.2.xx

Programming notes: Continued with all dose levels, timepoints and parameters

Template T_PK4

Table 14.2.xx Summary of log-transformed derived emodepside plasma pharmacokinetic parameters

Parameter	Treatment	{Additional time variables}	n	Geom Mean	95% CI (Lower,Upper)	SD (logs)	%CV _b
AUC _{last} (units)	Treatment 1 (N=xx)			xxxx.xx	(xxxx.xx,xxxx.xx)	xx.xxx	xx.xx
	Treatment 2 (N=xx)			xxxx.xx	(xxxx.xx,xxxx.xx)	xx.xxx	xx.xx
C _{max} (units)	Treatment 1 (N=xx)			xxxx.xx	(xxxx.xx,xxxx.xx)	xx.xxx	xx.xx
	Treatment 2 (N=xx)			xxxx.xx	(xxxx.xx,xxxx.xx)	xx.xxx	xx.xx

Source: Listing 16.2.xx

Programming notes: Continued with all dose levels, timepoints and parameters

Template T_AE1

Table 14.3.3.xx Summary of treatment-emergent adverse events

System Organ Class	Preferred Term	Treatment 1 (N=xx) n (%)	Treatment 2 (N=xx) n (%)	Etc
Number of subjects with AEs		x (xx.x)	x (xx.x)	
Gastrointestinal disorders	Total number of subjects	x (xx.x)	x (xx.x)	
	Abdominal discomfort	x (xx.x) [xx]	x (xx.x) [xx]	
	Abdominal pain	x (xx.x) [xx]	x (xx.x) [xx]	
	↓			
Nervous system disorders	Total number of subjects			
	Dizziness			
	Headache			
	↓			
	↓			

n = number of subjects (subjects with ≥1 adverse event are counted only once per system organ class and preferred term)

[] = number of adverse events

Based on MedDRA version xx.x

Source: Listing 16.2.xx

Programming notes: Continued with all treatment groups
 SOC and PTs are sorted in decreasing order of frequency
 Presented for all applicable MedDRA system organ classes and terms.

Template T_AE3

Table 14.3.3.xx Summary of treatment-emergent adverse events by severity

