2.1 Derived and transformed data

A list of those parameters that will be log transformed will be given in the SAP.

In general, concentration and concentration-related quantities, rate constants and half-lives (e.g. C_{max} , AUC, $t_{1/2}$, CL/F, V_z/F and MRT) will be analysed after logarithmic transformation. Logarithmic transformations will use natural logarithms (\log_e).

If t_{max} is subjected to a statistical analysis, it will not be transformed and will be analysed using non-parametric methods (Cartwright et al.(1991)).

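### The SAP's formula for the geometric between-subject CV squares the exponential instead of the SD, so as printed it overstates variability whenever SD(log) is below 2

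*SAP*

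**What the plan says.** SAP section 15 (Pharmacokinetic Analyses) defines the between-subject CV in two ways.

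- Formula 1, for untransformed data, is 100 times the ratio "SD/Mean)$ with SD and Mean of untransformed data".
- Formula 2, for log-transformed data, is 100 times the square root of "\exp(SD)^2 - 1}$ with SD of log-transformed data" (the stray symbols are typesetting code). The bracket after SD closes before the exponent.

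The log base is fixed in SAP Appendix B 2.1: "Logarithmic transformations will use natural logarithms". For log-transformed variables, section 15 also promises the geometric mean, "its 95% confidence interval and the SD of the logs will be provided".

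The results go to two templates in SAP 18.2.1. T_PK3, "Summary of derived emodepside plasma pharmacokinetic parameters", has a %CVb column beside the arithmetic mean and SD. T_PK4, "Summary of log-transformed derived emodepside plasma pharmacokinetic parameters", has a %CVb column beside SD (logs) and is used for Table 14.2.1.3. No other place in the SAP restates formula 2, and Protocol 10.7 lists %CV without a formula.

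**The concern.** Read literally, formula 2 is not the CV of a log-normal variable. A program written to it would put a wrong %CVb in Table 14.2.1.3 for every parameter that Appendix B marks for log transformation: Cmax, the AUCs, trough, λz, half-lives, clearance, volume and mean residence time.

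Tables 14.2.1.2 and 14.2.1.3 would then carry columns with the same label, for the same parameters and subjects, that differ severalfold with nothing to explain why. A reader who used the geometric column would see far more between-subject variability than the data contain. PK is a secondary objective, and the analysis after Cohorts 1 and 2 is meant to inform whether later-phase work goes ahead. Between-subject variability is a natural input to planning such studies.

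**Working it through.** **Inputs.** Formulas 1 and 2 come from SAP section 15, and natural logs from Appendix B 2.1. The documents give no numeric CV or SD(log), so there is no stated figure to reproduce. Protocol 1.4 describes exposure in the single-dose study only as "with low to moderate inter-individual variability". I therefore assume SD(log) from 0.1 to 0.5 and show values outside that range as well.

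**Algebra.** Write s for the SD of the natural-log values.

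- As printed: 100 × sqrt(exp(s)² − 1) = 100 × sqrt(exp(2s) − 1).
- Log-normal CV: 100 × sqrt(exp(s²) − 1).
- The printed form is larger when 2s > s², that is, when 0 < s < 2. The two are equal at s = 2 (both 732.1%), and the printed form is smaller above 2.
- For small s, exp(s²) − 1 ≈ s², so the log-normal CV tends to s, as it should, and agrees with formula 1. The printed form tends to sqrt(2s), which does not.

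**Worked case, s = 0.3.**

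- Log-normal: exp(0.09) = 1.0942; sqrt(0.0942) = 0.307, so 30.7%.
- As printed: exp(0.6) = 1.8221; sqrt(0.8221) = 0.907, so 90.7%.

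**Across the range.**

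| SD(log) | Log-normal CV | As printed | Ratio |
|---|---|---|---|
| 0.05 | 5.0% | 32.4% | 6.5 |
| 0.1 | 10.0% | 47.1% | 4.7 |
| 0.2 | 20.2% | 70.1% | 3.5 |
| 0.3 | 30.7% | 90.7% | 3.0 |
| 0.4 | 41.7% | 110.7% | 2.7 |
| 0.5 | 53.3% | 131.1% | 2.5 |
| 1.0 | 131.1% | 252.8% | 1.9 |
| 2.0 | 732.1% | 732.1% | 1.0 |
| 2.1 | 901.5% | 810.5% | 0.9 |

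Starting from the true CV instead, s = sqrt(ln(1 + CV²)). True CVs of 20%, 30% and 50% (s = 0.198, 0.294 and 0.472) would be reported as 69.7%, 89.4% and 125.4%.

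**Check against formula 1.** In 4 million simulated log-normal values, SD/Mean was 20.2%, 30.7% and 53.3% at s = 0.2, 0.3 and 0.5, matching the log-normal formula.

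**At this trial's cohort size.** The medians below are over 200,000 simulated samples of n = 6:

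| True SD(log) | Formula 1 | Log-normal form | As printed |
|---|---|---|---|
| 0.1 | 9.3% | 9.3% | 45.3% |
| 0.3 | 27.6% | 28.5% | 86.6% |
| 0.5 | 45.0% | 49.2% | 124.1% |

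So T_PK3 and a correctly computed T_PK4 would roughly agree, while T_PK4 as printed would not.

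**Effect on a later user.** Converting a reported CV back to a log-variance uses ln(1 + CV²). Applied to the printed form this returns 2s instead of s², an inflation of 2/s: 2/0.3 = 6.7-fold at s = 0.3 and 2/0.5 = 4-fold at s = 0.5.

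**The case against.** The strongest point is provenance. The whole defect is the position of one superscript in an equation that was read from a PDF by a program, and at least one other equation in this SAP seems to have been misread. In Appendix B 3.1.2 the formula for the extrapolated percentage of AUC shows an x where the row's own description, and the same formula in Protocol 8.4.2, have infinity. A displaced exponent is therefore possible. That does not show one: closing the bracket too early is also a common drafting slip. The documents available cannot settle which it is, and only the typeset page can.

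Second, harm requires literal programming. A PK statistician would recognise the intended formula, and Protocol 12.7 calls for validated SAS programs. But validating a program against a misprinted specification would not necessarily catch the error. If the code is already right, it departs from the signed plan, and SAP section 3 requires departures to be recorded in the study report.

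Third, the effect is descriptive and recoverable. SD (logs) stands in the adjacent column of T_PK4, no escalation rule uses the CV, and no sample size was calculated. A geometric value near 91% beside an arithmetic value near 31% would be conspicuous. All of this is true and limits how serious the point is, but it does not make the printed formula right.

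**Conclusion.** The concern holds as stated: formula 2, as it reads, is wrong for natural-log data and overstates %CVb whenever SD(log) is below 2. Over an assumed SD(log) of 0.1 to 0.5 the overstatement is about 4.7-fold falling to 2.5-fold; it is largest where variability is lowest.

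The conclusion rests on two conditions: that the typeset page has the exponent outside the bracket, and that the program follows the page. Confidence is medium because of the first. The consequence is confined to one descriptive column. Geometric means, their 95% intervals, SD (logs), the arithmetic %CVb and all safety results are unaffected. It should be fixed, but it does not threaten the trial's conclusions.

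**What to change.** 1. Look at formula 2 on the typeset page of SAP section 15. If it already shows exp(SD²), no SAP change is needed.
2. Otherwise replace it with %CVb = 100 × sqrt(exp(SD²) − 1), stating that SD is the standard deviation of the natural-log values.
3. In either case, check the program for T_PK4 (Table 14.2.1.3) against that form. A test input of SD(log) = 0.3 should return 30.7%.

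The cost is at most a one-line SAP correction and one program check. Nothing changes in data collection or in any other output.

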15.1 Plasma PK

15.1.1 Pharmacokinetic Concentration Data

The plasma concentrations of emodepside and metabolites (if applicable) will be listed and summarised by treatment.

Using actual sample times, linear and semi-logarithmic concentration-time plots of each analyte for each subject will be prepared. For subjects receiving more than one dose of a treatment, profiles will be included for all doses on the same plot. The same linear and logarithmic scales will be used for each subject. The linear and semi-logarithmic plots for a given subject will be presented on the same page. For clarity in presentation, individual profiles for different analytes will generally be separate.

Nominal blood sampling times will be used to calculate the geometric mean (geo SD) drug concentrations at each time point. Comparative linear and semi-logarithmic plots of the geometric mean (with geo standard deviation error bars) concentration-time data for each group will be prepared.

15.1.2 Pharmacokinetic Parameters

The pharmacokinetic parameters of emodepside and metabolites (if applicable) will be listed and summarised by treatment.

15.2 Urinary PK

If concentrations of emodepside and metabolites (if applicable) in urine are determined, the amount of emodepside excreted in the urine will be estimated and listed.

16 Pharmacodynamic Analyses

Summaries and listings will use the safety population.

Pharmacodynamic variables (glucose, insulin, glucagon, cortisol and oral glucose tolerance test) at each planned assessment, and change from baseline at each planned post-baseline assessment, will be summarised by treatment.

Individual PD subject profiles plotted against time will be presented for both absolute values and change from baseline.

17 References

1. International Conference on Harmonization, 1998. Statistical Principles for Clinical Trials - ICH Harmonised Tripartite Guideline. Guidance for Industry, E9, FDA federal register, Vol 63, 1998, p49583. Available at: <http://www.fda.gov/cder/guidance>.
2. International Conference on Harmonization, 1995. Structure and Content of Clinical Study Reports - ICH Harmonised Tripartite Guideline. Guidance for Industry, E3, FDA federal register, Vol 61, 1996, p37320. Available at: <http://www.fda.gov/cder/guidance>.
3. International Conference on Harmonisation, 2005. Clinical Evaluation of QT/QTc Interval Prolongation and Proarrhythmic Potential for Non-Antiarrhythmic Drugs. Concept paper, Guidance for Industry, E14, Center for Drug Evaluation and Research (CDER). Available at: <http://www.fda.gov/cder/guidance/6922fnl.htm>.
4. Julious, SA & Debnarot, CAM (2000) "Why are Pharmacokinetic Data Summarised by Arithmetic Means?", *Journal of Biopharmaceutical Statistics*, 10 (1), p55-71

18 ATTACHMENTS

18.1 Table of Contents for Data Display Specifications

For overall page layout refer to Appendix C.

Tables, figures and listings will be labelled A (for Cohorts 1 and 2) and B (for Cohort 3), e.g. 14.1A, 14.1B. Separate tables will be produced for Cohorts 1 and 2 and for Cohort 3.

The numbering in the tables below will take precedence over the numbering in the shells.

The following tables and figures will be produced (templates provided in Section 18.2.1):

Table	Description	Population	Source Listing	Template (Shells below)
10.1	Summary of subject disposition	Safety	16.2.1.2, 16.2.3.1	T_SD1
14.1	DEMOGRAPHIC DATA			
14.1	Summary of demographic characteristics	Safety	16.2.4.1	T_DM1
14.2	PHARMACOKINETIC AND PHARMACODYNAMIC DATA			
14.2.1.1	Summary of emodepside plasma pharmacokinetic concentration-time data [units]	PK Concentration	16.2.6.1.1	T_PK1
14.2.1.2	Summary of derived emodepside plasma pharmacokinetic parameters	PK Parameter	16.2.6.1.2	T_PK3
14.2.1.3	Summary of log-transformed derived emodepside plasma pharmacokinetic parameter	PK Parameter	16.2.6.1.2	T_PK4
14.2.2.1	Summary of glucose	Safety	16.2.6.2.1	T_LB2
14.2.2.2	Summary of insulin	Safety	16.2.6.2.1	T_LB2
14.2.2.3	Summary of glucagon	Safety	16.2.6.2.1	T_LB2
14.2.2.4	Summary of cortisol	Safety	16.2.6.2.1	T_LB2
14.2.3.1	Summary of oral glucose tolerance test results	Safety	16.2.6.2.1	T_LB2
14.3	SAFETY DATA			
14.3.1.1	Summary of treatment-emergent adverse events	Safety	16.2.7.1	T_AE1
14.3.1.2	Summary of drug-related treatment-emergent adverse events	Safety	16.2.7.1	T_AE1
14.3.1.3	Summary of treatment-emergent adverse events by severity	Safety	16.2.7.1	T_AE3
14.3.2.1	Listing of fatal adverse events	Safety	16.2.7.1	L_AE1_PG
14.3.2.2	Listing of non-fatal serious adverse events	Safety	16.2.7.1	L_AE1_PG
14.3.2.3	Listing of other significant adverse events	Safety	16.2.7.1	L_AE1_PG
14.3.3	Narratives of deaths, other serious and significant adverse events	Safety		-
14.3.4	Summary of laboratory values of potential clinical importance	Safety	16.2.8.1, 16.2.8.3	T_LB1
14.3.5.1	Summary of chemistry laboratory values	Safety	16.4	T_LB2
14.3.5.2	Summary of haematology laboratory values	Safety	16.4	T_LB2
14.3.5.3	Summary of coagulation laboratory values	Safety	16.4	T_LB2
14.3.5.4	Summary of urinalysis results	Safety	16.2.8.5	T_UR1

Table	Description	Population	Source Listing	Template (Shells below)
14.3.6.1	Summary of vital signs	Safety	16.4	T_VS1
14.3.7.1	Summary of ECG values	Safety	16.4	T_EG2
14.3.7.2	Summary of ECG values and changes in ECG values of potential clinical importance	Safety	16.2.9.2	T_EG3

Figure	Description	Population	Source Listing	Template (Shells below)
14.2	PHARMACOKINETIC AND PHARMACODYNAMIC DATA			
14.2.1.1	Individual emodepside plasma concentration-time plots (linear and semi-log)	PK Concentration	16.2.6.1.1	F_PK1
14.2.1.2	Geometric mean (with geo SD error bars) emodepside plasma concentration-time plots (linear and semi-log)	PK Concentration	16.2.6.1.1	F_PK2
14.2.2.1	Individual glucose-time plots	Safety	16.4	F_SAF1
14.2.2.2	Individual insulin-time plots	Safety	16.4	F_SAF1
14.2.2.3	Individual glucagon-time plots	Safety	16.4	F_SAF1
14.2.2.4	Individual cortisol-time plots	Safety	16.4	F_SAF1
14.3	SAFETY DATA			
14.3.1	Individual systolic blood pressure-time plots	Safety	16.4	F_SAF1
14.3.2	Individual diastolic blood pressure-time plots	Safety	16.4	F_SAF1
14.3.3	Individual heart rate-time plots	Safety	16.4	F_SAF1
14.3.4	Individual QTcF-time plots	Safety	16.4	F_SAF1
14.3.5	Individual QTcB-time plots	Safety	16.4	F_SAF1

The following abbreviated listings will be produced (templates provided in Section 18.2.2):

Listing	Description	Template (Shells below)
16.2.1	Study dates & disposition of subjects	
16.2.1.1	Listing of study dates	L SD1 PG
16.2.1.2	Listing of reasons for withdrawal	L SD2 PG
16.2.2	Protocol deviations	
16.2.2.1	Listing of subjects with inclusion/exclusion criteria deviations	L DV1 PG
16.2.2.2	Listing of subjects with time deviations	L TD1 PG
16.2.2.3	Listing of subjects with other protocol deviations	L DV2 PG
16.2.3	Analysis sets, including subjects excluded from analysis	
16.2.3.1	Listing of analysis populations	L AN1 PG
16.2.4	Demographic data & concomitant medication	
16.2.4.1	Listing of demographic characteristics	L DM1 PG
16.2.4.2	Listing of concomitant medications	L CM1 PG
16.2.5	Study drug administration	
16.2.5.1	Listing of exposure data	L EX1 PG
16.2.6	Pharmacokinetic and pharmacodynamic data	
16.2.6.1.1	Listing of emodepside plasma pharmacokinetic concentration-time data	L PK1 PG
16.2.6.1.2	Listing of derived emodepside plasma pharmacokinetic parameters	L PK4 PG
16.2.6.1.3	Listing of emodepside plasma urine sample collections	L PK2 PG
16.2.6.1.4	Individual emodepside plasma concentration-time plots for estimation of λ_z , with regression line	F PK10
16.2.6.2.1	Listing of PD concentration-time data	L PK1 PG
16.2.7	Adverse events	
16.2.7.1	Listing of all adverse events	L AE1 PG
16.2.7.2	Listing of serious adverse events	L AE1 PG
16.2.7.3	Listing of adverse events leading to withdrawal from study	L AE1 PG
16.2.8	Laboratory values	
16.2.8.1	Listing of clinical chemistry abnormalities of potential clinical importance	L LB1 PG
16.2.8.2	Listing of all clinical chemistry laboratory data for subjects with PCI	L LB2 PG

Listing	Description	Template (Shells below)
	abnormalities*	
16.2.8.3	Listing of haematology abnormalities of potential clinical importance	L LB1 PG
16.2.8.4	Listing of all haematology laboratory data for subjects with PCI abnormalities*	L LB2 PG
16.2.8.5	Listing of urinalysis data	L URI PG
16.2.9	Vital signs, ECG variables and physical findings	
16.2.9.1	Listing of vital signs of potential clinical importance	L VS1 PG
16.2.9.2	Listing of ECG values of potential clinical importance	L EG1 PG
16.2.9.3	Listing of abnormal ECG findings	L EG2 PG
16.2.9.4	Listing of abnormal physical examination findings	L PE1 PG
16.2.9.5	Listing of abnormal neurological examination findings	L NE1 PG
16.2.9.6	Listing of abnormal ophthalmology examination findings	L PE1 PG

* ICH does not require full listings of lab data so only subjects with double-flagged values will be listed.

Complete listings of all data collected in this study will also be produced.

